6.3. AESI Definition and Conventions

The AESI consist of a list of preferred terms grouped by specific category (for example, pulmonary events, gastrointestinal events categories) and/or by subcategory (for example, diabetes). These categories and subcategories are defined based on MedDRA, and the list that is most current at the time of analysis will be used. Also, changes may be made to this list with each new version of MedDRA.

6.4. Time-to-Onset Definition

Time-to-onset of AESI (any grade) for a specific category (for example, pulmonary events, gastrointestinal events) is defined as the time between the day of the first dose of study drug and the onset date of the earliest AESI (of any grade) in this category.

Time-to-onset of AESI (Grade 3-5) for a specific category is defined similarly but restricted to Grade 3-5 AESI.

Time-to-onset of drug-related (Grade 3-5 or any grade) AESI for a specific category is defined similarly but restricted to drug-related AESI.

Time-to-onset for a specific subcategory is defined similarly but restricted to events in this subcategory.

6.5. Time-to-Resolution Definition

In order to derive the time-to-resolution, overlapping or contiguous AESI within a specific category will be collapsed into what will be termed “clustered” AESI. For example, if a subject (without pre-treatment AE) experienced an AE from 01 January to 05 January, another AE (with different PT but within same category) from 06 January to 11 January, and the same AE from 10 January to 12 January, these will be collapsed into one clustered AESI from 01 January (onset date) to 12 January (resolution date). Table 13 summarizes key derivation steps for each type of clustered select AEs.

Time-to-resolution of AESI (any grade) for a specific category is defined as the longest time from onset to complete resolution or improvement to the grade at baseline among all AESI clusters in this category experienced by patients. Events which worsened into Grade 5 events (death) or have a resolution date equal to the date of death are considered unresolved. If a clustered AESI is considered to be unresolved, the resolution date will be censored to the last known alive date. Improvement to the grade at baseline implies that all different AE events in the clustered AESI should at least have improved to the corresponding (that is, with same preferred term) baseline grade (or improve to lower grade). Time-to-resolution is defined only for subjects who experienced at least one AESI in the specific category.

The time-to-resolution of AESI (Grade 3-5) for a specific category is defined similarly with an onset date corresponding to a Grade 3-5 AESI.

Time-to-resolution of drug-related AESI (any grade or Grade 3-5) is defined similarly but restricted to drug-related AESI.

Time-to-resolution for a specific subcategory is defined similarly but restricted to events of this subcategory.

Table 13. Derivation of Clustered AESI

Type of clustered select AE	Derivation
Any grade	Collapse any on-treatment AESI from the same category
Drug-related of any grade	Collapse any on-treatment drug-related AESI from the same category
Grade 3-5	Collapse any on-treatment AESI from the same category. Resolution will be based on the onset date of the earliest Grade 3-5 records (clusters with only Grade 1-2 should not be selected)
Drug-related of Grade 3-5	Collapse any on-treatment drug-related AESI from the same category. Resolution will be based on the onset date of the earliest Grade 3-5 record (clusters with only Grade 1-2 should not be selected)

Abbreviations: AE=adverse event; AESI=adverse event of special interest.

The algorithm for collapsing selected AE records is using the following conventions. For each patient and specified category, the corresponding AE records will be collapsed when:

- Multiple AE records have the same onset date.
- The onset date of an event record is either the same day or 1 day later than the resolution date of a preceding event record (contiguous events).
- The onset date of an event record is after the onset date and prior to or on the resolution date of a preceding event record (overlapping events).

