9.2.5. Follow-up of Adverse Events

Any ongoing AEs should be followed until the earliest occurrence of one of the following:

- The AE has resolved or stabilized
- Completion of safety follow-up visit
- Start of new antitumor therapy
- Withdrawal of consent

- Death
- Other (eg, transfer to another hospital)

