5. STATISTICAL ANALYSIS

5.1. General Methods

All recorded data will be presented in listings.

The categorical data will be summarized using frequency counts and percentages of patients. The continuous data will be summarized using number of non-missing observation (n), mean, standard deviation, median, minimum and maximum unless otherwise specified.

Summary tables will be presented by cohort. Data listings will be presented with patient ID and cohort.

For concomitant medications/therapy and adverse events, the cycle number is determined based on their start/onset dates. For other collected data, the cycle number is determined based on their visit dates. These data include Lab test, Physical exam, Vital signs, Height and Weight, Ophthalmological exam, ECOG, ECG, Pregnancy test, Tumor biopsies, Scheduled tumor assessment.

When there are multiple laboratory records for a scheduled visit, the one closest to the target date will be used for analysis. If there are two or more records with the same time period to the target date, the record with the latest database entry date will be used for analysis.

Time to event distribution, PFS, OS, DoR, time to onset of adverse event of special interest (AESI) in a specific category, and time to resolution of AESI in a specific category, will be estimated using Kaplan–Meier techniques. The number of events and censorings will be reported. When appropriate, the median along with the corresponding log-log transformed 95% CI will be estimated. Rates at fixed time points will be derived from the Kaplan-Meier estimate and corresponding confidence interval will be derived based on Greenwood formula for variance derivation and on log-log transformation applied on the survivor function $S(t)$. Confidence intervals for binomial proportions, ORR and DCR, will be derived using the Clopper–Pearson method.

All the analyses of efficacy, safety, and pharmacodynamics data for this study will be performed using SAS® statistical software package, Version 9.3 or a higher version.

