5.5.2.6. Adverse Events of Special Interest

Incidence

AESI will be summarized:

- Summary of AESI with the number and percentage of patients reporting AESI, serious AESI, grade ≥ 3 AESI, AESI leading to study drug discontinuation, interruption and dose reduction, and AESI with outcome of deaths.
- Summary of AESI by worst CTCAE grade (grade 1, 2, 3, 4, 5, any grade, Grade ≥ 3) presented by category or subcategory / PT

A by-patient listing of AESI will also be provided.

Time to Onset

Time-to-onset of selected AESI (e.g. hyperphosphatemia) will be summarized for each category/subcategory of AESI.

- Time-to-onset of any grade AESI
- Time-to-onset of Grade ≥ 3 AESI

Time-to-onset analyses are restricted to treated patients with at least one specific event.

The derivation of time-to-onset of AESI is detailed in Section 6.4.

Time to Resolution

Time-to-resolution of selected AESI (e.g. hyperphosphatemia) will be summarized.

- Time-to-overall resolution of AESI
- Time-to-resolution of Grade ≥ 3 AESI (overall and until \leq Grade 2)

The following summary statistics will be reported: percentage of subjects who experienced the specific events, percentage of subjects with resolution of the AESI (clustered), median, 1st quartile and 2nd quartile of time-to-resolution along with 95% CI (derived from Kaplan-Meier estimation) and ranges.

Time-to-resolution of Grade ≥ 3 AESI (e.g. hyperphosphatemia) will be graphically displayed using the Kaplan-Meier technique.

Time-to-resolution analyses are restricted to patients who experienced the specific events. Collapsing selected AE and derivation of time-to-resolution of AESI is detailed in Section 6.5.

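### Censoring deaths in the Kaplan-Meier analysis of AESI time to resolution biases the Grade ≥3 resolution curve, and any fixed-time resolution rate, upward; minor, and fixable with a cumulative incidence estimate

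*SAP*

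**What the plan says.** SAP 6.5 defines time to resolution per patient and AESI category, as the longest time to resolution among that patient's clusters. On death it says: "Events which worsened into Grade 5 events (death) or have a resolution date equal to the date of death are considered unresolved". The next sentence gives the handling: "If a clustered AESI is considered to be unresolved, the resolution date will be censored to the last known alive date". There is no separate rule for patients who have died.

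SAP 5.1 names the estimator: "time to resolution of AESI in a specific category, will be estimated using Kaplan–Meier techniques". The same paragraph adds, for time-to-event endpoints in general, "Rates at fixed time points will be derived from the Kaplan-Meier estimate".

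SAP 5.5.2.6 lists the statistics to report, among them "percentage of subjects with resolution of the AESI (clustered), median, 1st quartile and 2nd quartile of time-to-resolution along with 95% CI (derived from Kaplan-Meier estimation"). It plans a plot for Grade ≥3 AESI only, which "will be graphically displayed using the Kaplan-Meier technique". The analysis set is given as: "Time-to-resolution analyses are restricted to patients who experienced the specific events". Patients whose AESI was fatal are therefore included.

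Neither document provides a competing-risk estimate for this endpoint.

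**The concern.** Kaplan-Meier takes a censored patient's share of the sample and spreads it over those still at risk, on the footing that the censored patient could have resolved later at the same rate. That is reasonable for a living patient whose follow-up has stopped. It is not reasonable for a patient who has died, because death rules out resolution. SAP 6.5 correctly says a fatal AESI is not a resolution, but the censoring and the estimator then let that patient contribute to a rising resolution curve.

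The effect is most visible in the Grade ≥3 plot, because Grade 5 events enter the Grade 3-5 clusters by definition. An AESI category with more deaths could show a curve rising just as high as one with none. A table giving the crude percentage resolved and the curve for the same patients could also disagree in one report.

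The problem does not depend on choosing the right censoring dates: it remains even if every date is correct.

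**Working it through.** The documents state no expected AESI resolution time, fatality rate or resolution proportion, so there is no planned figure to reproduce. What follows is illustration.

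**Small examples.** Suppose 10 patients have the AESI, 9 resolve, and 1 dies of it before the last resolution.
- Crude proportion resolved: 9/10 = 90%.
- Kaplan-Meier with the death censored: at the last resolution only that one patient is at risk, so the unresolved fraction is multiplied by 1 − 1/1 = 0 and the curve reaches 100%.

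In a constructed set of 20 patients (16 resolved, 4 died unresolved at days 8, 15, 22 and 30), the Kaplan-Meier curve ends at 100%. Cumulative incidence and the crude percentage both give 16/20 = 80%. The median is 21 days either way; the third quartile is 32 days by Kaplan-Meier and 42 days when deaths count as never resolved.

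**Continuous-time illustration.** Inputs:
- Median time to resolution of 30, 60 or 90 days: assumed.
- Median survival of 12 to 15 months (365 or 456 days): Protocol 1.1, where it describes platinum-treated advanced disease. Applying it here is an assumption, because this trial enrols patients who are not platinum candidates.
- Constant hazards: resolution rate r = ln 2 / median resolution time; death rate d = ln 2 / median survival.

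Formulas:
- Kaplan-Meier with deaths censored: 1 − exp(−r·t).
- Cumulative incidence with death competing: r/(r + d) × [1 − exp(−(r + d)·t)].
- Standard error (SE) with n affected patients: √[CIF(1 − CIF)/n], where CIF is the cumulative incidence.

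| Resolution median | Day | Kaplan-Meier | Cumulative incidence | Gap (points) | Gap in SE, n = 10 |
|---|---|---|---|---|---|
| 30 d | 90 | 87.5% | 82.7–83.6% | 3.9–4.8 | 0.3–0.4 |
| 60 d | 90 | 64.6% | 60.3–61.1% | 3.5–4.4 | 0.2–0.3 |
| 90 d | 90 | 50.0% | 46.4–47.1% | 2.9–3.6 | 0.2 |
| 30 d | 180 | 98.4% | 91.4–92.7% | 5.7–7.1 | 0.7–0.8 |
| 60 d | 180 | 87.5% | 78.3–80.0% | 7.5–9.2 | 0.6–0.7 |
| 90 d | 180 | 75.0% | 66.0–67.6% | 7.4–9.0 | 0.5–0.6 |

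With 25 affected patients the gap would be 0.3 to 0.6 SE at day 90 and 0.8 to 1.3 SE at day 180. Output is by cohort and cohorts hold 20 to 26 patients, so 25 would require nearly every patient in a maximal cohort to have the AESI. Ten is the more realistic illustration.

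**Quantiles, same inputs.** The median moves from 30 to 30.9–31.2 days, from 60 to 63.8–64.9, and from 90 to 99–102. The first quartile moves from 12.5 to 12.6 days in the 30-day case and from 37.4 to 38.6–38.9 in the 90-day case.

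**Sensitivity to the share that dies.** With resolution medians of 14 to 28 days and 2% to 30% of affected patients dying unresolved (all assumed), the day-90 gap runs from 1.3 to 29 points. With no such deaths it is zero.

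**The case against.** A reader might infer that the trial's reported proportion of AESIs resolved will be overstated. The documents do not support that. SAP 5.5.2.6 lists the percentage of subjects with resolution as its own statistic, apart from the Kaplan-Meier quantiles. Its natural denominator is patients who experienced the event, and fatal events are unresolved by rule. Read as a crude proportion it gives 90% in the ten-patient example, which is correct. The SAP gives no formula for it, but nothing ties it to the Kaplan-Meier curve. The unit is also the patient within a category, not each AESI.

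A reader might also infer that the Kaplan-Meier curve is too high overall. Only the death component has a known sign. Living patients with unresolved AESIs are also censored at the last known alive date, while Protocol 9.2.5 ends AE follow-up sooner in many cases: "Any ongoing AEs should be followed until the earliest occurrence of one of the following". Those patients stay in the risk set when resolution is no longer recorded, which pulls the curve down. That is a separate matter and does not justify censoring deaths, but it means the net direction is not established.

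Further points stand:
- SAP 5.5.2.6 names no fixed time point for AESI resolution and no upper quartile. The quantiles it does list move little or modestly, so the visible bias is largely in the Grade ≥3 plot.
- The only AESI it names as an example is hyperphosphatemia, which Protocol 1.3.2 describes as mostly low grade and without clinical complications. Deaths caused by that event should be rare, although other categories may be selected and deaths from any cause count.
- Fatal AESIs are already tabulated (SAP 5.5.2.6, with deaths and AEs leading to death in 5.5.2.1 and 5.5.2.2). Deaths from other causes with an AESI still open are not.
- The analysis is descriptive, with no test or decision attached, and does not touch the primary ORR analysis.

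None of this answers the core point: followed as written, the SAP treats dead patients as still able to resolve.

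**Conclusion.** The point holds for the Kaplan-Meier outputs. Censoring patients who die with an unresolved AESI, including a fatal one, biases the Grade ≥3 resolution curve and any fixed-time resolution rate upward, and shortens the quantiles slightly. It does not extend to the separately listed percentage with resolution if that is crude, or to a claim about the net direction of all the censoring taken together.

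The size depends on how many patients die unresolved and cannot be set from the documents. Under the assumed constant hazards it is 3 to 5 points at day 90 and 6 to 9 points at day 180, under one standard error with 10 affected patients. Severity is minor.

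**What to change.** In SAP 5.1, 5.5.2.6 and 6.5:
- Estimate time to resolution, per patient and category, by the cumulative incidence function (Aalen-Johansen), with death while the AESI is unresolved as a competing event.
- Censor only patients who are alive and unresolved.
- Take the median as the time at which the cumulative incidence reaches 50%, and report it as not reached if it never does.
- Report the number of patients who died, from any cause, with the AESI unresolved.
- State that the percentage of subjects with resolution is a crude proportion of patients who experienced the event.

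The cost is SAP wording, a standard competing-risk procedure and a little more programming. No new data are needed and clinical conduct does not change. The resolution figures become slightly less favourable.

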3.2.2.1. Safety Follow-Up Period and 30-Day Safety Follow-Up Visit

The safety follow-up period is the time from the date of last dose of study therapy through the safety follow-up visits, which must be performed 30, 60 and 90 days (± 3 days) following the last dose of study therapy. If the patient starts new anticancer therapy within 30 days of the last dose of study therapy, the 30-day safety follow-up visit should be performed before the start of new anticancer therapy. Every effort should be made to perform the assessments outlined in [Table 1](#). If the patient is unable to return to the study site, a follow-up phone call can be made by the study site to collect any new safety information that occurred during the safety follow-up period.

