3.2.4. Survival Follow-up

Once disease progression is confirmed or new anticancer therapy is initiated, whichever occurs first, the survival follow-up period begins. During this period, the patient or family should be contacted for survival follow-up every 12 weeks (± 2 weeks) until patient withdraws consent or the study is terminated early by the Sponsor. In addition, all subsequent anticancer treatments will be recorded.

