9.3.2. Repeat Testing

Evaluation of any clinically significant laboratory test will be repeated, as clinically indicated, until the value returns to the baseline level or clinically stabilizes, or until another treatment is given.

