9.4.2. Reporting of Serious Adverse Events (within 24 hours)

All SAEs occurring from the time the ICF is signed through the Safety Follow-up Period (90 days after the last dose of study drug or discontinuation of the Safety Follow-up Period, whichever is earlier) must be reported to Sponsor's Pharmacovigilance group or its designee **within 24 hours** from the time the Investigator first becomes aware of the SAE.

Comprehensive information available at the time of initial reporting (including narrative description, medical history, and concomitant medications) needs to be provided with careful consideration regarding causality and serious criterion. The SAE reporting process and contact information are provided in supplement guidelines.

After the initial SAE notification to the Sponsor's Pharmacovigilance group or its designee, all follow-up SAE information will be submitted each time they become available (for example, clinical diagnosis, outcome, causality assessment, results of specific investigations) on a follow up SAE form. The Investigator also must submit further information if it is required by the Sponsor or the director of the study site or an institutional review board (IRB)/independent ethics committee (IEC). Every SAE should be followed until it has resolved, stabilized, or returned to baseline.

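### SAP 6.5 censors unresolved AESIs at the last known alive date, which can fall after AE follow-up has ended, and the protocol gives incompatible rules for AE capture after day 30

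*SAP*

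**What the plan says.** **Censoring.** SAP 6.5 sets the rule for an AESI cluster that has not resolved: "If a clustered AESI is considered to be unresolved, the resolution date will be censored to the last known alive date". SAP 5.5.2.6 applies Kaplan-Meier to these times, reports "median, 1st quartile and 2nd quartile of time-to-resolution along with 95% CI", and plots Grade 3 or higher AESIs. Hyperphosphatemia is the only AESI it names for this analysis.

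**AE follow-up.** Protocol 9.2.5 says: "Any ongoing AEs should be followed until the earliest occurrence of one of the following". Its list includes resolution or stabilization, completion of the safety follow-up visit, and "Start of new antitumor therapy". Protocol 3.2.2.1 has three such visits: "safety follow-up visits, which must be performed 30, 60 and 90 days" after the last dose. SAEs have their own rule in Protocol 9.4.2: "Every SAE should be followed until it has resolved, stabilized, or returned to baseline". For laboratory findings, Protocol 9.3.2 adds: "Evaluation of any clinically significant laboratory test will be repeated, as clinically indicated, until the value returns to the baseline level or clinically stabilizes". Repeat testing also stops there once the patient receives a different therapy.

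**Survival follow-up.** Under Protocol 3.2.4, "the patient or family should be contacted for survival follow-up every 12 weeks" (±2 weeks) after progression or new therapy.

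**Capture of new AEs.** The Schedules of Events (Protocol Tables 1 and 2, SAP Table 1), Protocol Section 6 with 9.1, and Protocol 3.2 each state a window. They differ after day 30, as set out in the working.

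**The concern.** A censoring date should be the last date on which the event could have been recorded. A survival contact establishes that the patient is alive, not whether a rash or an eye finding has cleared. If an AESI was last assessed at day 30 after the last dose and the patient is known alive a year later, the SAP counts that year as observed, unresolved time.

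The capture conflict has two consequences. Sites that follow different sections would collect different events, and analysis cannot recover events never collected. The conflict also leaves open where observation of an unresolved AESI ends, which is the date a correct censoring rule needs. Safety is a secondary objective, so this concerns the duration of toxicity and the content of the safety database, not the primary endpoint.

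**Working it through.** The plan gives no figure to reproduce here. The clustering example in SAP 6.5 (01-05, 06-11 and 10-12 January collapsing to 01-12 January) is correct, so the issue is only the censoring date.

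**1. Direction.** Kaplan-Meier multiplies factors (1 − d/n), with d resolutions among n at risk. Take five patients: three resolve on days 10, 20 and 40, and two are unresolved with AE follow-up ending on days 15 and 30 and last known alive 84 days later (days 99 and 114).

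| Day | Unresolved share, censored at end of AE follow-up | Unresolved share, censored at last known alive |
|---|---|---|
| 10 | 4/5 = 0.80 | 4/5 = 0.80 |
| 20 | 0.80 × 2/3 = 0.533 | 0.80 × 3/4 = 0.60 |
| 40 | 0.533 × 0/1 = 0 | 0.60 × 2/3 = 0.40 |

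A later censoring time can only leave the curve unchanged or raise it.

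**2. Size, base model.** All inputs are assumptions:
- treatment duration exponential, median 150 days; further survival exponential, median 240 days;
- resolution exponential;
- onset by day 14 (early) or uniform over treatment;
- data cut-off uniform, 183 to 730 days after first dose;
- new therapy in 0%, 30% or 60% of patients, starting 14 days plus an exponential time (median 30 days) after the last dose.

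Resolution is seen only up to the earliest of the end of AE follow-up, new therapy, death and cut-off. Medians in days under the SAP rule (300,000 patients per scenario), early / uniform onset:

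| AE status known to | New therapy | True 60 | True 90 | True 180 |
|---|---|---|---|---|
| Day 30 | 0% | 64 / 71 | 104 / 155 | 305 / not reached |
| Day 30 | 60% | 64 / 73 | 105 / 159 | not tabulated |
| Day 90 | 0% | 60 / 60 | 90 / 90 | 206 / 362 |
| Day 90 | 60% | 61 / 63 | 95 / 102 | not tabulated |

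Repeat runs give about 64-74 and 104-166 for the day-30 rows. Censoring at the end of AE follow-up returns true medians of up to 90 days to within about 1 day.

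**3. Dependence on the model.** In the base model, true medians of 14 and 30 days read correctly. A second model lets AE follow-up end at an exponential time after onset (mean 30, 60 or 120 days), so it can end much sooner. Then a true 14 reads 15.2-21.7, a true 30 reads 36.2, 49.9 or not reached, and a true 60 reads 96.6-98.1, 218 or not reached.

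**4. Noise.** With 20 AESI patients and a true median of 60, the 5th-95th percentiles of the estimate (SAP rule against end of AE follow-up, no new therapy) are:
- day 30, early onset: 31-116 against 31-105;
- day 30, uniform onset: 31-not reached against 31-127 (median not reached in 10% against 1% of trials);
- day 90, early onset: 31-96 against 31-96;
- day 90, uniform onset: 32-104 against 32-103.

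**5. Which earlier date.** Protocol 9.2.5 also stops follow-up at stabilization. Suppose a share p stabilizes (median 30 days) and never resolves, the rest resolve with median 60 days, and nobody starts new therapy. The true median is (60/ln 2) × ln[(1 − p)/(0.5 − p)]: 84.9 days for p = 0.2 and 108.4 for p = 0.3.

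| p, AE status known to | True | SAP rule | Censored at last status, including stabilization | Censored at end of scheduled AE follow-up |
|---|---|---|---|---|
| 0.2, day 90 | 85 | 84-85 | 70 | about 85 |
| 0.3, day 90 | 108 | 110-111 | 77 | 108-109 |
| 0.2, day 30 | 85 | 98 (early), about 150 (uniform) | 70-71 | 85-86 |

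Censoring at stabilization is informative and makes toxicity look shorter than it is.

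**6. Capture rules side by side.**

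| Event, days after last dose | Schedules of Events | Protocol Section 6 and 9.1 | Protocol 3.2 |
|---|---|---|---|
| Rule | AEs to day 90 or new therapy | all AEs to day 30 or new therapy; SAEs to day 90; related SAEs through survival follow-up (9.1) | after the 30-day visit, related SAEs only, if no new therapy |
| Non-serious AE, day 45 | collected | not collected | not assessed |
| Unrelated SAE, day 45 | collected | collected | not assessed |

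Protocol 9.1 attaches the term safety follow-up to the 30-day point, whereas 3.2.2.1 runs that period through day 90. The visit that closes AE follow-up in 9.2.5 is therefore undefined.

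**The case against.** The best defence is that few AESIs are exposed. SAEs are followed beyond the ordinary AE rule. Hyperphosphatemia is covered by chemistry at the 30-, 60- and 90-day visits and by repeat testing. Protocol Table 5 has Grade 3 and 4 eye toxicities reported as SAEs, and Protocol 6.1 monitors retinal pigment epithelial detachment every 2 to 3 weeks. SAP 6.3 does not itemize the AESI terms, so no clearly exposed event can be named. If AE status is known to day 90 and nobody starts new therapy, the bias is nil up to a true median of 90 days. This stands, and it limits the point to slow-resolving, mainly non-serious AESIs. It does not make the rule right: an AESI that is still open when AE follow-up closes is given follow-up time that nobody observed.

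A second objection is that moving the censoring date to the last AE assessment could do more harm than the present rule. Step 5 bears this out where AESIs stabilize without resolving, and the fix is worded accordingly.

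A reader might also infer that the SAP's 30-day AE tables are wrong because SAEs are collected to day 90. The documents do not support that. The synopsis bases safety on treatment-emergent AEs, the SAP defines these by a 30-day window, and later SAEs and deaths are still listed.

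**Conclusion.** Both parts hold. The SAP 6.5 censoring date can lie beyond the period in which resolution is recorded, and the resulting bias lengthens time to resolution. Its size cannot be fixed from the documents. It ranges from nil to moderate for true medians of 60 to 90 days in the base model, is larger if follow-up ends soon after onset, and is often within sampling noise for a cohort. The main exception is AE status that ends at day 30 with onsets spread over treatment.

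A reader might infer from the base model that medians of 30 days or less are always safe, or that reported durations will be badly wrong. Neither follows: the second model shifts short medians, and several scenarios show no bias.

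The capture conflict needs no assumptions and is the firmer of the two parts. ORR is unaffected. The change should be made, but the trial's main conclusion does not depend on it.

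**What to change.** **(a) SAP 6.5.** Censor an unresolved AESI at the end of scheduled AE follow-up: the earliest of the safety follow-up visit that closes AE follow-up, new antitumor therapy, withdrawal of consent, death and data cut-off. For an SAE, use the last SAE follow-up date if later. Keep an AESI that stabilized without resolving at risk to that same date, and do not censor it at stabilization. This treats a stabilized AESI as unresolved until a resolution is recorded, which the SAP should say. Cost: one changed censoring date and somewhat fewer patients at risk at late times.

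**(b) Protocol.** Reconcile 3.2, Section 6, 9.1 and the Schedules of Events (with SAP Table 1) into one capture rule. State in 9.2.5 which of the day 30, 60 or 90 visits ends AE follow-up, and how this fits with SAE follow-up in 9.4.2. Part (a) needs that visit named. Cost: a protocol amendment, with approval by the Investigator and IRB/IEC documented as Protocol 12.3 requires.
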